#### **4.2.2 Safety Laboratory data**

Measurements below the limit of quantification (BLQ) will be imputed with half of the lower limit of quantification (LLOQ) for the purpose of calculating change from Baseline and descriptive statistics.

Measurements above the limit of quantification (ALQ), if applicable, will be imputed to the upper quantification limit for the calculation of changes from baseline and descriptive statistics. These rules will be applied to all safety laboratory data including clinical chemistry and urinalysis.

Descriptive statistics will be calculated if at most 33% of the individual data points at a timepoint are missing or are either not quantifiable (<LLOQ) or ALQ. Values that are BLQ will be replaced by the numerical value of the LLOQ/2 in this instance and values that are ALQ will be imputed to the value of the upper quantification limit. If more than 33% of the individual data points at a timepoint are missing or not quantifiable (BLQ and/or ALQ), no descriptive statistics will be calculated.

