## **14.4 Other analyses**

### **14.4.1 Safety analyses**

The incidence of subjects with TEAEs will be determined by treatment group. Furthermore, the absolute and relative frequencies for subjects with a given TEAE with respect to the preferred term according to the latest available version of the Medical Dictionary for Regulatory Activities (MedDRA®), will be determined within each treatment group and system organ class. Additional tables will summarize TEAEs by maximum severity and causal relationship with rozanolixizumab, as judged by the investigator, per treatment group. Adverse events will be categorized by severity according to the National Institutes for Health (CTCAE) version 4.03 grading (National Institutes for Health, 2009). In case the CTCAE grading is not available, the intensity (mild/moderate/severe) will be utilized. The TEAEs leading to discontinuation of IMP and the serious TEAEs will also be summarized by treatment group. The action taken, time of onset relative to dosing, actual dose received, and duration of each AE will be listed only.

For the continuous laboratory variables, the values and changes from Baseline will be descriptively summarized by treatment group at each time point. For categorized values according to the reference range, shift tables from Baseline to each post-Baseline time point will be presented for selected variables to be defined in the SAP. Values outside the reference range will be flagged in the data listings.

Descriptive statistics will be presented for ECG value and changes from Baseline by treatment group and over time based on the mean of the triplicate assessments at each time point. Categorical analyses for QTc, eg, QTc increase >60msec, will also be performed.

Descriptive statistics will be reported for all vital sign measurements (including BP, PR, temperature, and body weight). Measured values and changes from Baseline will be summarized by treatment group and by time point.

Physical and neurological examination findings and the results of any pregnancy testing will be presented in listings only. Results will be listed for any subjects who complete a headache questionnaire, undergo stool sampling, or lumbar puncture, etc.

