### **14.4.2 PK analyses**

Pharmacokinetic variables of rozanolixizumab like AUC (area under the curve),  $C_{\max}$  (maximum concentration) cannot be derived, since blood sampling will be performed at 1 time point post-dosing per visit only. Thus, PK is restricted to concentration data.

In contrast to the general descriptive display, concentration data will be summarized by treatment group, actual dose received, and time point using the number of available observations, mean,

median, SD, minimum, maximum, geometric mean (and associated 95% confidence intervals), and geometric coefficient of variation (assuming log-normally distributed data). Values below the lower limit of quantification (LLOQ) will be reported with a clear sign indicating that they were below the LLOQ. Descriptive statistics of concentrations will be calculated if at least two-thirds of the individual data points are quantifiable ( $\geq$ LLOQ). Individual concentrations of rozanolixizumab will also be displayed graphically.

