## 2.4 Determination of sample size

Due to the pilot character of the study, the sample size is chosen based on both the statistical considerations and practical limitations (eg, to recruit sufficient subjects in a reasonable time to achieve the objectives of the study) and to establish whether a positive trend towards active treatment can be established. For this reason, a one-sided exploratory test is considered appropriate in this setting.

Since no data is currently publicly available on the primary outcome measure in this indication, the sample size is based on assumptions about the likely effect size. Thus, the sample size considerations are only based on assumptions for the effect size index (difference in group means/SD). When the sample size in each group is 15, a 1-sided 5.0% t-test for the comparison of rozanolixizumab and placebo will provide 80% power to detect a statistically significant difference in case there is a large effect of rozanolixizumab with an effect size index of 0.93. In case of a medium index (0.52) the power already decreases to 40%. It will be assumed that 10% of the randomized subjects cannot be utilized for the efficacy analysis; hence 34 subjects will be randomized.

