## 3 DATA ANALYSIS CONSIDERATIONS

### 3.1 General presentation of summaries and analyses

Statistical evaluation for the final analyses will be performed by PAREXEL. The Analysis Dataset Model (ADaM) will adhere to Clinical Data Interchange Standards Consortium (CDISC) guidance documents and follow their UCB interpretation.

All analyses will be performed using SAS version 9.4 or higher (SAS Institute, Cary, North Carolina, USA). Continuous variables will be summarized by treatment group (Placebo and rozanolixizumab) and visit (where applicable) with the statistics mean, standard deviation (SD), median, minimum, and maximum. Categorical variables will be summarized by treatment group and visit (where applicable) with frequency counts and percentages. Geometric coefficient of variation (geoCV), geometric mean (geoMean) and 95% Confidence Interval (CI) for the geoMean will also be presented in the descriptive statistics for the PK concentration.

When reporting relative frequencies or other percentage values, the following rules apply:

- For values where all participants fulfill certain criteria, the percentage value will be displayed as 100
- For values where the absolute frequency is zero, there will be no percentage displayed at all
- All other percentage displays will use 1 decimal place
- Percentages displayed based on continuous data (eg, percentage changes from baseline) will be displayed to 1 decimal place.

When reporting descriptive statistics, the following rules will apply in general:

- n will be an integer
- Mean (arithmetic and geometric), SD and median will use 1 decimal place more than the original data
- Coefficient of variation and geoCV will be reported as a percentage to 1 decimal place
- Minimum and maximum will be reported using the same number of decimal places as the original value

---

- If no participants have data at a given timepoint, for example, then only n=0 will be presented. If n<3, then only n, minimum and maximum will be presented. If n=3, then only n, mean, median, minimum and maximum will be presented. The other descriptive statistics will be left blank.

Analyses will be performed by treatment group and for all participants where stated. The treatment groups will be displayed as follows in the TFLs:

- Treatment group 1: Placebo
- Treatment group 2: Rozanolixizumab

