#### **4.2.3 Pharmacodynamic data**

Measurements BLQ are not anticipated for the total serum IgG data. In the event that any BLQ measurements are received, these will be regarded as missing for the calculation of descriptive statistics and changes from Baseline.

Descriptive statistics will be calculated if at most 33% of the individual data points at a timepoint are missing or are either not quantifiable (<LLOQ) or ALQ as described in Section 4.2.2.

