## 9 PHARMACOKINETICS AND PHARMACODYNAMICS

### 9.1 Pharmacokinetics

Pharmacokinetic variables of rozanolixizumab like AUC (area under the curve),  $C_{\max}$  (maximum concentration) cannot be derived, since blood sampling will be performed at 1 time point post-dosing per visit only. Thus, PK is restricted to concentration data.

Concentration data will be summarized for treatment rozanolixizumab by exposure (%) categories (see section 10.1) and time point using the number of available observations, mean, median, SD, minimum, maximum, geoMean, (and associated 95% confidence intervals), and geoCV (assuming log-normally distributed data) based on the PK-PPS.

Concentration data will be summarized for treatment rozanolixizumab by time point and █ status (6 classifications; see Section 9.3.2) using the number of available observations, mean, median, SD, minimum, maximum, geoMean, (and associated 95% confidence intervals), and geoCV (assuming log normally distributed data) based on the PK-PPS.

Individual concentrations of rozanolixizumab as well as planned and actual dose administered will be listed by treatment group for the SS and summarized for the PK-PPS, and will include the actual sampling time in days relative to the previous dose.

The following rules will apply for PK data listings and summaries:

- Values below the LLOQ will be reported as BLQ.
- Descriptive statistics of concentrations will be calculated if at most 33% of the individual data points at a timepoint are missing or are not quantifiable (<LLOQ). Values that are BLQ will be replaced by the numerical value of the LLOQ/2 in this instance. However, if  $n \leq 3$ , then only n, minimum and maximum will be presented as summary statistics. The other descriptive statistics will be left blank. If more than 33% of data points is missing then no summary statistics are given, irrespective of n.
- If no participants have data, only  $n=0$  will be presented. The other descriptive statistics will be left blank.
- The 95% CI lower and 95% CI upper should be left blank if the SD (or equivalently, the geoCV) is 0
- The geoCV will be calculated using the following formula where SD is the standard deviation from the log-transformed data

$$\text{geoCV (\%)} = \sqrt{[\exp(\text{SD}^2) - 1]} \times 100$$

For each participant, individual concentration versus time (week) profiles will be presented graphically in linear and semi-logarithmic scale. In addition, combined individual (spaghetti

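### The SAP's 33% rule counts missing samples as well as unquantifiable ones, with no denominator defined, so valid visit-level laboratory, IgG and immunology summaries can be withheld

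*SAP*

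**What the plan says.** SAP 4.2.2 (safety laboratory data) puts absent values and values outside the assay limits (below, BLQ, or above, ALQ) into one count: "If more than 33% of the individual data points at a timepoint are missing or not quantifiable (BLQ and/or ALQ), no descriptive statistics" are produced. SAP 4.2.3 (pharmacodynamic data) and 4.2.4 (immunological data) each repeat the condition and refer back to 4.2.2: "Descriptive statistics will be calculated if at most 33% of the individual data points at a timepoint are missing", with unquantifiable results again added to the count. SAP 9.1 goes further for drug concentrations: "If more than 33% of data points is missing then no summary statistics are given, irrespective of n". For total IgG, 4.2.3 does not expect BLQ results, and if any occur "these will be regarded as missing for the calculation of descriptive statistics and changes from Baseline".

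The protocol is narrower. Its only threshold of this kind is in 14.4.2 and concerns PK assay results: "Descriptive statistics of concentrations will be calculated if at least two-thirds of the individual data points are quantifiable". For laboratory data, Protocol 14.4.1 sets no threshold: "For the continuous laboratory variables, the values and changes from Baseline will be descriptively summarized by treatment group at each time point". Protocol 14.4.3 and 14.4.4 set none for PD or immunology. SAP 3.9, which lists changes to protocol-defined analyses, does not mention the extension.

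SAP 3.1 already has a display rule for sparse data: "If n<3, then only n, minimum and maximum will be presented", with mean and median added when n=3.

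**The concern.** A quantifiability threshold has a clear purpose: when many results are censored by the assay, a mean built on substituted values misleads. That reasoning does not carry over to participants who gave no sample. The values from those who did are still valid, and showing n tells the reader how many there are.

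This design is expected to produce absences. Relapse in the Treatment Period stops IMP and moves the participant to a premature-end-of-treatment (PEOT) visit and then stabilization visits. There, laboratory samples come only every 4 to 6 weeks and no IgG sample is listed (Protocol Table 5-1 and 8.3.3). Completers without relapse may enter the open-label extension (OLE) at Visit 17, which is then their last visit. What is at stake is the visit-level summary of laboratory change (a safety variable), of total IgG (a secondary objective) and of the immunological variables.

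**Working it through.** **Arm size.** SAP 2.4 starts from 15 per group: "When the sample size in each group is 15, a 1-sided 5.0% t-test" has 80% power at effect size 0.93 and 40% at 0.52. An exact non-central t calculation (28 degrees of freedom, 1-sided 5%) gives 79.9% and 39.9%, so those figures reproduce. Allowing 10% non-evaluable, 30/(1 − 0.10) = 33.3, rounded up to 34. At 1:1 this is 17 per arm, the planned size for laboratory and immunology tables, which use the Safety Set. PD summaries use a subset of the Full Analysis Set and may rest on fewer.

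**Where the rule bites.** The smallest k with k/n > 0.33:

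- n = 17: 5/17 = 29.4% is shown; 6/17 = 35.3% is suppressed, with 17 − 6 = 11 valid values unshown.
- n = 15: 4/15 = 26.7% is shown; 5/15 = 33.3% is suppressed on a literal 33%, although 10/15 meets a two-thirds criterion. This case turns only on whether 33% is a rounded third.
- Both arms pooled, n = 34: 11/34 = 32.4% is shown; 12/34 = 35.3% is suppressed. Six absences in one arm alone (6/34 = 17.6%) would not trigger it.
- Samples obtained as denominator: if all 11 are quantifiable, 0/11 = 0% and nothing is suppressed.

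The SAP does not say which denominator applies, and the same data give different tables.

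**Against the small-n rule.** In a 17-participant arm, n = 3 means 14/17 = 82.4% missing. On the by-arm reading the 33% rule has already blanked a whole-arm table at n = 11, so the n<3 and n=3 displays in SAP 3.1 are never reached.

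**How likely.** The documents give no relapse or OLE uptake rate, so the missing probability p at a visit is an assumption. With independent participants, P(X ≥ 6) = Σ C(17,k) p^k (1−p)^(17−k), summed over k = 6 to 17:

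| Assumed p | P(arm of 17 crosses the limit) |
|---|---|
| 10% | 0.5% |
| 20% | 10.6% |
| 30% | 40.3% |
| 40% | 73.6% |
| 50% | 92.8% |

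**Which visits.** Relapse or withdrawal can thin the later Treatment Period visits. Direct OLE entry can thin laboratory tables at Visits 19 and 21, and IgG, IgA/IgE/IgM and vaccine titres at Visit 21. Complement and cytokines are sampled only to Visit 16 and PK only to Visit 17, so direct OLE entry does not affect them.

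**The case against.** The strongest reply is that the denominator is open. A direct OLE entrant has no Visit 19 or 21 sample scheduled, so calling that value missing is an interpretation; the word could mean a scheduled sample that was lost or unusable. This stands in part: suppression is not certain. But the SAP names missing separately from unquantifiable. Where it wants absent samples left out, it says so: the immunogenicity prevalence summary in 9.3.2 excludes them from the denominator, and the QTcF categories in 10.4.2 use non-missing measurements. SAP 4.2.2 to 4.2.4 contain no such wording. For total IgG, where BLQ results are not expected, absence is the realistic trigger.

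It is also fair that the sentence making suppression independent of n appears only in the PK section, so it cannot prove the intent elsewhere. It does show that, for PK, missingness alone suppresses output.

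A reader might go further and infer three things that the documents do not support:

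- That Visit 19 and 21 tables will be empty. This needs more than about a third of an arm without samples, and uptake is not stated.
- That the arm with more relapses loses its summaries first. Direct OLE entry is open only to those who complete treatment without relapse, so after Visit 17 it acts more on the arm with fewer relapses. Treatment-period relapsers keep a Final Visit with laboratory and IgG sampling (Protocol Table 8-1 and 8.3.2). SAP 4.3 also maps PEOT values, and later visits on the Observation schedule, to planned visits.
- That the between-arm IgG comparison disappears. Each participant's minimum IgG and maximum decrease are summarized by arm from all available data (SAP 9.2.1), and direct OLE entry leaves IgG through Visit 17 intact.

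Listings with out-of-range and marked-abnormality flags (SAP 10.3) and the liver-injury table (10.3.1) also remain.

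**Conclusion.** The point holds as a defect in a stated rule, with a bounded effect. Missingness counts towards suppression in four SAP sections, the denominator is undefined, and the extension beyond the protocol's PK quantifiability rule is not disclosed in SAP 3.9. On the plain by-arm reading, six absences among 17 withhold 11 valid values.

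How often this happens rests on rates that the documents do not give; it is negligible at 10% missing and near certain at 50%. The figures assume 17 per arm, independent participants and a by-arm denominator. Visit-level descriptive summaries are exposed; the primary and other efficacy analyses are not. The change should be made because withholding valid safety and IgG values on account of other participants' absence has no evident statistical purpose.

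**What to change.** In SAP 4.2.2, 4.2.3, 4.2.4 and 9.1:

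- Apply the 33% limit only to the share of BLQ or ALQ results among samples obtained in each treatment group at that timepoint, and state that denominator.
- Delete missing data as a trigger, including the sentence in 9.1 that suppresses output whatever the value of n.
- Always show n and descriptive statistics for available data, subject to the small-n display rules in 3.1 (and those in 9.1 for PK).
- Record in 3.9 that the threshold goes beyond the protocol's PK rule.

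In the 6-of-17 example, the 11 observed values would then be summarized. The cost is SAP wording, with no extra data. The small downside is that some late-visit summaries will rest on a selected subset, which the displayed n makes visible.

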#### **4.2.3 Pharmacodynamic data**

Measurements BLQ are not anticipated for the total serum IgG data. In the event that any BLQ measurements are received, these will be regarded as missing for the calculation of descriptive statistics and changes from Baseline.

Descriptive statistics will be calculated if at most 33% of the individual data points at a timepoint are missing or are either not quantifiable (<LLOQ) or ALQ as described in Section 4.2.2.

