#### 4.2.4 Immunological data

The rules for handling BLQ or ALQ measurements for all immunological data will be as described in Section 4.2.2.

Descriptive statistics will be calculated if at most 33% of the individual data points at a timepoint are missing or are either not quantifiable (<LLOQ) or ALQ as described in Section 4.2.2.

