### **9.2.1 Total Serum IgG**

Total Serum IgG concentrations and IgG subclasses will be listed by treatment group and timepoint including absolute changes from Baseline and percentage changes from Baseline. Descriptive summaries (including n, arithmetic mean, median, SD, minimum and maximum) will be presented by treatment group and timepoint for absolute values, changes from Baseline and percentage changes from Baseline.

Further descriptive summaries (including n, arithmetic mean, median, SD, minimum and maximum) will be presented by treatment group, timepoint and █ status (6 categories; see Section 9.3.2) for absolute values, changes from Baseline and percentage changes from Baseline.

Participant total Serum IgG will be plotted against planned time. Mean Serum IgG, mean change from Baseline and percentage change from Baseline will be plotted against planned time by treatment group.

For each participant, the minimum value and maximum decrease (absolute and percentage) from Baseline in total serum IgG concentration during the study (using all available data up to cut-off point) will be listed. The minimum value and maximum decrease will be summarized by treatment group. In the event that a decrease from Baseline in IgG is not observed in a given participant, the maximum decrease will be reported as the smallest increase from Baseline.

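### SAP 4.2.3 drops PD results below quantification as missing, which would understate the IgG reduction if any occur, and the SAP leaves unclear which BLQ rule governs

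*SAP*

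**What the plan says.** SAP 4.2.3 has two paragraphs. The first says "Measurements BLQ are not anticipated for the total serum IgG data" and adds that if any are received, "these will be regarded as missing for the calculation of descriptive statistics and changes from Baseline". The second allows descriptive statistics at a timepoint only if at most 33% of the data points "are missing or are either not quantifiable (<LLOQ) or ALQ as described in Section 4.2.2".

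The corresponding paragraph of SAP 4.2.2 (safety laboratory data) sets the same 33% limit and says: "Values that are BLQ will be replaced by the numerical value of the LLOQ/2 in this instance". SAP 4.2.4 says: "The rules for handling BLQ or ALQ measurements for all immunological data will be as described in Section 4.2.2". SAP 4.2.5 also uses half the LLOQ for drug-concentration summaries.

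SAP 6.2 lists total IgG and its subclasses among the immunological variables for the baseline summaries, while SAP 9.2 analyses them as PD. SAP 9.2.1 reports for each participant "the minimum value and maximum decrease (absolute and percentage) from Baseline in total serum IgG concentration during the study", from all available data, with no BLQ rule of its own. Total IgG carries a secondary objective (Protocol 3.2).

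**The concern.** The drug is meant to lower IgG. Protocol 5.4.4 expects maximum mean reductions above 70%. A BLQ result is therefore not an uninformative gap: it says that the value lies below every quantified one. Treating it as missing makes missingness depend on the outcome, and the error runs one way. The mean level is too high, the mean change and percentage change are too small, and a maximum decrease computed from changes falls back to the lowest quantifiable visit. This happens mainly in the arm where IgG is driven down.

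Two further matters affect how the rule would be programmed. PD is the only numeric laboratory domain in SAP 4.2.2 to 4.2.5 that deletes BLQ values in its summaries, and no reason is given. In addition, one IgG assay can be placed under 4.2.3 (missing) or, through the label in 6.2, under 4.2.4 (LLOQ/2), so two programmers could produce different tables from the same data.

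**Working it through.** **Inputs.** From the documents: the BLQ rules above, the 33% limit, an expected maximum mean reduction above 70% (Protocol 5.4.4), and 15 per group (SAP 2.4). Not in the documents, so assumed: the LLOQ (0.5, 1 or 2 g/L) and baseline IgG (10 or 14 g/L). The plan has no figure of its own to reproduce here.

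**Step 1: how far IgG must fall to be BLQ.** Required reduction = 100 × (1 − LLOQ/baseline).
- Baseline 10 g/L: 95% at LLOQ 0.5, 90% at LLOQ 1, 80% at LLOQ 2.
- Baseline 14 g/L: 96.4%, 92.9% and 85.7%.

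A 70% fall from 10 g/L leaves 3.0 g/L. An average responder stays quantifiable; only the deep tail is exposed.

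**Step 2: how many BLQ values can enter a summary.** With 15 participants, 4 BLQ (26.7%) pass the 33% limit and 5 (33.3%) do not. With 17, 5 (29.4%) pass and 6 (35.3%) do not. Values missing for other reasons use up the same allowance.

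**Step 3: the two rules at n = 15.** Take baseline 10 g/L and every quantifiable value at −70%. The missing rule gives −70.0% whatever the BLQ count k. The LLOQ/2 rule gives [(15 − k) × (−70) + k × c]/15, with c = −95 at LLOQ 1 (0.5 g/L left) and c = −90 at LLOQ 2 (1 g/L left).
- LLOQ 1: k = 1 gives (−980 − 95)/15 = −71.7%; k = 2, −73.3%; k = 3, −75.0%; k = 4, −76.7%.
- LLOQ 2: −71.3%, −72.7%, −74.0%, −75.3%.
- k = 0: the rules agree.

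The truth can be bounded. At LLOQ 1 a BLQ value means a fall of 90 to 100%, so with k = 1 the true mean lies between (−980 − 90)/15 = −71.3% and (−980 − 100)/15 = −72.0%. The missing rule is then 1.3 to 2.0 points short; LLOQ/2 is within about 0.3 either way.

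**Step 4: expected bias.** Simulation with 400,000 draws per scenario. Baseline is normal, 10 (SD 2.5) or 14 (SD 4) g/L, floored at 3. Reduction is independent and normal, 70% (SD 8), 75% (SD 8) or 80% (SD 6), limited to 0 to 98%. Bias is in percentage points of mean percentage change.

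| Baseline, reduction | LLOQ 1: BLQ | missing understates | LLOQ/2 overstates | LLOQ 2: BLQ | missing understates | LLOQ/2 overstates |
|---|---|---|---|---|---|---|
| 10, 70% | 1.7% | 0.3 | 0.1 | 18.8% | 1.9 | 1.4 |
| 10, 75% | 5.3% | 0.8 | 0.2 | 33.9% | 3.5 | 1.8 |
| 10, 80% | 8.9% | 0.8 | 0.3 | 53.5% | 3.9 | 2.3 |
| 14, 70% | 0.9% | 0.1 | 0.1 | 7.7% | 0.8 | 0.5 |
| 14, 75% | 2.8% | 0.4 | 0.1 | 16.1% | 1.7 | 0.7 |
| 14, 80% | 4.2% | 0.4 | 0.1 | 26.7% | 1.9 | 1.1 |

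At LLOQ 0.5 g/L or below, at most about 1.1% of values are BLQ and the missing rule is off by at most about 0.2 points. At LLOQ 2, the 3.5 and 3.9 come from scenarios whose expected BLQ share exceeds 33%, where the summary would often be suppressed; in the other four the range is 0.8 to 1.9. In no scenario is the LLOQ/2 error larger than that of the missing rule.

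**Step 5: subclasses and NF-L.** Both are summarised as PD (SAP 9.2.1 and 9.2.2). The sentence on what is anticipated names only total serum IgG. The documents give neither an LLOQ nor an expected level for these assays, so no size can be put on them.

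**The case against.** The strongest reply is that the rule is a contingency the SAP does not expect to use, and that all PD output is descriptive in a pilot study. SAP Table 13-2 supports the first part: a marked-abnormality limit of IgG at or below 1 g/L suggests, without proving it, that the assay reads down to about that level. This stands for total IgG and is why the size is conditional. It does not cover subclasses or NF-L, and a contingency rule should still be sound when it is triggered.

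A reader might infer that 4.2.3 flatly contradicts 4.2.2. The documents do not establish that. The cross-reference is attached to the 33% limit, and the imputation in 4.2.2 is scoped by "These rules will be applied to all safety laboratory data including clinical chemistry and urinalysis". SAP 4.2.4 shows how the BLQ rule is imported when that is intended: it has a separate sentence for it, which 4.2.3 lacks. The natural reading is that only the limit is borrowed. Even so, the paragraph referred to contains the LLOQ/2 replacement, and the SAP never says that part is excluded. That is an ambiguity to settle.

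A reader might also infer that the deepest reductions vanish from view and that a participant's nadir is hidden from safety review. That is not supported either. The rule is limited to descriptive statistics and changes; all documented data are listed (SAP 3.1), IgG is listed by timepoint (9.2.1), and the interim patient profiles plot observed IgG (SAP 11). IgG is sampled at every dosing visit, so a summary minimum would fall back to the lowest quantifiable value. The listed individual minimum is not expressly covered by the missing rule.

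Finally, LLOQ/2 has a bias of its own in the opposite direction. True; its size is in the table.

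**Conclusion.** The point holds in conditional form. If PD values fall below quantification, SAP 4.2.3 removes them because they are low, and the mean and maximum decrease in IgG are understated, mainly on active treatment. For total IgG the effect is nil if no value is BLQ, as the SAP anticipates. Otherwise it is about 0.1 to 0.8 percentage points at an LLOQ of 1 g/L and 0.8 to 3.9 at 2 g/L, with the 33% limit often suppressing the summaries at the top of that range. These figures rest on an assumed LLOQ, baseline and spread of response, none of which is in the documents.

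The more practical exposure is IgG subclasses and NF-L. SAP 4.2.3 is the only section headed for PD data, it states no BLQ expectation for these assays, and it does not say outright whether its missing rule reaches them. The matter is worth correcting because it touches a secondary objective and the choice of rule is unclear. It does not affect the primary efficacy analysis.

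**What to change.** In SAP 4.2.3, replace the sentence that treats BLQ results as missing with one rule: BLQ values of total serum IgG, IgG subclasses and NF-L are set to LLOQ/2 for summaries, changes, percentage changes, minimum value and maximum decrease. Add two statements. First, the number of BLQ values is reported for each treatment group and timepoint. Second, the reference to 4.2.2 covers only the 33% limit, under which no statistics are given if "more than 33% of the individual data points at a timepoint are missing or not quantifiable". With the same rule in 4.2.3 and 4.2.4, the double labelling of IgG no longer matters.

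The cost is a few SAP sentences and one extra count in the PD tables; no new data are needed. The downside is that LLOQ/2 can overstate the mean reduction, by about 0.1 to 0.3 points at an LLOQ of 1 g/L and 0.5 to 2.3 at 2 g/L on the same assumptions. The BLQ counts let a reader see where that could matter.
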